#### 7.4 (P4) Recruitment Discussion (N=100)

**A. Audio-recording and upload (N=100)**

- a. DIVI team has script for consent to audio-record consent discussion**
- b. DIVI team member to retrieve iPad from [redacted]**
  - i. iPad will be passcode protected**
  - ii. Passcode will be provided to consenting DIVI study team members only**
- c. Once the tablet is unlocked, two icons will be present on the home screen**
  - i. Voice Memos app**
  - ii. Link to REDCap**
- d. Using the Voice Memos app**
  - i. Open Voice Memos app**
  - ii. Tap the record button (red circle) to begin recording**
  - iii. Tap the pause button (two vertical red bars) to stop recording**
  - iv. Tap “Done” to save the recording**
  - v. Renaming the recording**
    - 1. Tap the name at the top of the screen (the default name is typically “New Recording X”)**
    - 2. Enter the [DIVI screening ID]**
    - 3. Tap “return” on the keyboard**
    - 4. Tap “Done” on the bottom right corner of the screen**
  - vi. Tap the more options button at the top of the screen (Circle with three dots)**
  - vii. Tap “Share...”**
  - viii. Tap “Save to files”**
  - ix. Tap “On My iPad”**
  - x. Select “BRIEF Consent Audio”**
  - xi. Tap “Save”**
- e. Return to home screen and open link to REDCap survey**
  - i. Enter DIVI screening ID**
  - ii. Select your name from the list of DIVI Team Members**
  - iii. If the Consent Discussion was recorded, select “Yes”**
  - iv. Tap “Upload file”**
  - v. Tap “Choose File”, tap “Choose File” again**
  - vi. Navigate to the “BRIEF Consent Audio” folder**
    - 1. If not in the BRIEF Consent Audio folder already, tap “Browse” in the upper left-hand corner**
    - 2. Tap “On My iPad”**
    - 3. Tap the “BRIEF Consent Audio” file**
    - 4. Tap the recording**
  - vii. Tap “Upload file”**
  - viii. Complete short milestones format survey about consent discussion that just took place**
- f. Close both the Voice Memos and the REDCap link and turn off the tablet**
- g. Return tablet to [redacted]**

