Better Research Interactions for Every Family

Statistical Analysis Plan

Project # 3469

[name]

6/1/2022

A feasibility study for an educational intervention to improve equity and respect in recruitment conversations with families who are eligible for a neonatal clinical trial. A pre-post study design will be used. Approximately 200 parents of eligible infants will be approached for consent, half using the current recruiting protocol ("pre") and half using the novel intervention ("post"). Conversations will be administered by 6 members, some of whom will administer more conversations than other members.

A subsample of these conversations will be recorded (n_record). This will be split equally between "pre" and "post" periods. Each recorded recruitment conversation will then be assessed by 3 experts (2 independent, and the member who administered the educational content). They will fill out a questionnaire (approximately 15 questions) answered with a Likert score. These questions fit into logical groupings to assess different aspects of equity and respect during the recruitment conversation.

The number of observations will be the number of conversations recorded multiplied by 3 (n_record*3). There are several sources of correlation between these observations (recruitment conversation, member administering the recruitment conversation, expert making the assessment) and so GEE will be used to estimate the intervention effect on each question and test the null hypothesis of no effect.

Analysis Plan

Descriptive statistics will be used to summarize eligible parents who engaged in conversations. Frequencies and percentages will be reported as appropriate for categorical variables. Means, medians, and standard errors will be calculated for continuous variables. Outcomes (5-point Likert scale) will be summarized in each intervention arm at the question level, as a total across all questions, and totals within each pre-defined question subgroup.

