At the question level, ordinal logistic regression will be used to assess the effect of the intervention on the distribution of scores. Models will be fit using generalized estimating equations (GEE) to account for correlation among results assessed on the same conversation. Results will be reported as intervention odds ratios and 95% confidence intervals. To test the overall effect of the intervention on the score (and in each subgroup of questions) we take the total of the question scores to be continuous and use GEE to fit standard linear regression to test the mean effect of intervention.

Models above assume each conversation administer has the same mean outcome and that experts evaluate themselves the same as others. These two assumptions will be evaluated and GEE models adjusted as needed. Further, since we plan to run many statistical tests (15 questions individually, score totals, subgroups), the p-value threshold to determine significance will be adjusted using Holm's method to control the family-wise type I error rate.

List of Figures/Tables

Figure 1: Flow diagram showing sample size allocation in pre/post cohort, exclusion, and number of videos sampled for assessment.

Figure 2: Distributions of scores in pre/post cohorts for each question, question totals and subgroups.

Figure 3: Estimated odds ratios and confidence intervals and of the pre/post effect tested for each question.

Table 1: demographics of those approached vs videos sampled.

Table 2: Likert score outcomes (counts, percentages) in pre/post, intervention odds ratio, 95% CI's and p-values for each question.

Table 3. Outcome totals (Mean, SD, IQR) and subgroups, estimates of mean effects (95% CIs) .

Power calculations

To assess statistical power, we pair simulation with calculations based on cluster randomized trial designs with a continuous outcome. These equations assume a mixed effects model consistent with the GEE methods used above and depend on the assumed effect size, outcome standard deviation, and intra-cluster correlation. To achieve 80% power at a 0.05 level when the true mean difference is 5 and standard deviation of 5, 8 videos (with 3 observations) need to be recorded per trial arm ($8*3*2 = 48$ total observations) if the intra-recording correlation is low ($\rho = 0.1$) while 15 recordings are needed per trial arm ($15*3*2 = 90$ total observations) if intra-recording correlation is high ($\rho = 0.8$).

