Input parameters were selected based on simulated ordinal 5-level data (with a uniform distribution across levels) generated 15 times (one for each question) to get totals across many realizations. This leads to an approximate distribution of total scores with mean 45 and standard deviation 5.

References

Heagerty, P.J. and Zeger, S.L. (1996) Marginal regression models for clustered ordinal measurements. *JASA*, **91** 1024–1036.

Matthews JNS. Introduction to Randomized Controlled Clinical Trials (2nd Ed.) Chapman & Hall: New York, 2006.

Donner A and Klar N. Design and Analysis of Cluster Randomization Trials in Health Research. Arnold: London, 2000.

Holm, S. (1979). A simple sequentially rejective multiple test procedure. *Scandinavian Journal of Statistics*, **6**, 65–70.
<https://www.jstor.org/stable/4615733>.

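### The SAP's 80% power at 8 or 15 recordings per arm ignores its own Holm adjustment; at those sizes the adjusted test of the total score has about 35–41% power (16 to 21 tests assumed)

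*SAP*

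**What the plan says.** The SAP (Power calculations) gives the recordings needed as follows: "To achieve 80% power at a 0.05 level when the true mean difference is 5 and standard deviation of 5, 8 videos" per arm with three ratings each at an intra-recording correlation (rho) of 0.1, and 15 per arm at rho 0.8. The outcome is the total over 15 questions. The inputs come from simulated uniform five-level answers: "This leads to an approximate distribution of total scores with mean 45 and standard deviation 5".

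The SAP (Analysis Plan) tests the total and each subgroup total by linear GEE, and each question by ordinal GEE. On multiplicity it says: "since we plan to run many statistical tests (15 questions individually, score totals, subgroups), the p-value threshold to determine significance will be adjusted" by Holm's method, to control the family-wise error. It names no primary test outside this family and does not give the number of subgroups.

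The SAP's opening summary leaves the number of recordings open as n_record, split equally between periods, and adds: "Each recorded recruitment conversation will then be assessed by 3 experts". Protocol section 7.4 plans 100 audio-recorded discussions. It also notes that "DIVI team has script for consent to audio-record consent discussion", so a family can decline to be recorded.

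**The concern.** The power section and the multiplicity rule use different thresholds for the same test. Power is computed as if the total score were tested alone at 0.05. Under the Analysis Plan, the total must clear a Holm threshold that starts at 0.05 divided by the number of tests, which is at least 16 (15 questions plus one total).

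The 8 and 15 are the only recording numbers the SAP ties to power. If recording fell short and the study ended near them, the SAP would support a claim of 80% power that the planned analysis does not have.

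**Working it through.** **Inputs.** From the SAP: mean difference 5, SD 5, three ratings per recording, rho 0.1 or 0.8, equal arms, level 0.05, target power 80%. Assumed: a two-sided test (one-sided gives 5 and 11 by the normal formula, which does not match), and 0 to 5 subgroup totals, so 16 to 21 tests.

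**Formula.** With n recordings per arm, the standard error of the difference is sqrt(2·SD²·(1 + 2·rho)/(3n)). The noncentrality is 5 divided by this. Power is from the noncentral t distribution with 2n − 2 degrees of freedom.

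- n = 8, rho 0.1: sqrt(2·25·1.2/24) = 1.581; noncentrality 3.162; df 14.
- n = 15, rho 0.8: sqrt(2·25·2.6/45) = 1.700; noncentrality 2.942; df 28.

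**The SAP's own figures.** At 0.05, power is 83.6% with 8 per arm (77.5% with 7) and 81.0% with 15 (78.1% with 14). So 8 and 15 are exactly the smallest sizes that reach 80% for one unadjusted test, with little to spare.

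**Power at Holm's first step, SD 5**

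| Tests | Threshold | 8 per arm, rho 0.1 | 15 per arm, rho 0.8 |
|---|---|---|---|
| 1 | 0.05 | 83.6% | 81.0% |
| 16 | 0.05/16 = 0.0031 | 39.2% | 40.5% |
| 18 | 0.05/18 = 0.0028 | 37.4% | 38.9% |
| 21 | 0.05/21 = 0.0024 | 35.1% | 36.9% |

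**Do later Holm steps rescue it?** The total gains only if other tests are rejected before it. If the 5-point shift is spread evenly (1/3 point per question; an assumption), each question has about 11–12% power at 0.05 (question SD 5/sqrt(15) = 1.29), so few precede the total. The full step-down was simulated for 16, 19 and 21 tests with between-question correlation 0 to 0.6. The total was rejected in 36–42% of runs (8 per arm) and 38–43% (15 per arm). Even at 0.05/6, the threshold after ten of 16 tests have been rejected, power is only 55% at both sizes.

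**Recordings per arm for 80% power at Holm's first step, SD 5**

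| Tests | rho 0.1 | rho 0.8 |
|---|---|---|
| 16 | 14 (80.9%) | 28 (81.6%) |
| 21 | 15 (82.4%) | 29 (81.1%) |

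**Sensitivity to the SD.** A uniform 1-to-5 score has variance (25 − 1)/12 = 2. If the 15 questions are independent, the total has SD sqrt(15·2) = 5.48, which the SAP gives as approximately 5. At SD 5.48:

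- One test at 0.05: power is 77% and 74% at 8 and 15 per arm; 80% needs 9 and 18.
- First Holm step: power is 31% and 32% (16 tests) or 27% and 28% (21 tests); 80% needs 17 and 33, or 17 and 34.

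**At the planned size.** With 100 recordings (50 per arm) and rho 0.8, first-step power is 99% at SD 5 and 96–97% at SD 5.48, for 16 to 21 tests.

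**The case against.** **The figure depends on the method.** The SAP plans GEE and names no t reference. A normal reference gives 58–55% (8 per arm) and 49–46% (15 per arm) for 16 to 21 tests. An uncorrected robust Wald test would reject more often still, about 66–63% and 55–52%, partly because its type I error is inflated at such small sizes. This stands as a caveat on precision. It does not restore 80%. The normal formula also gives 7 and 14, not 8 and 15, unless one cluster per arm is added, whereas the t method gives the SAP's sizes directly.

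**The range describes Holm's first step.** Correct: the full procedure adds about 0 to 3 points.

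**The sentence is true as written.** It says 0.05, and at 0.05 the sizes are right. But 0.05 is not the threshold the SAP sets for the total, and nothing in the power section says so.

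**The consequence is hypothetical.** This largely stands. The Protocol plans 100 recordings, and neither document projects a fall to 16 or 30. Protocol section 2 gives the aims as feasibility, preliminary experience and effect estimates, so no confirmatory decision rests on this test, and estimates with confidence intervals are reported in any case. That limits the severity. It does not remove the mismatch, because the SAP itself chose formal tests, family-wise error control and a power claim.

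**Conclusion.** The concern holds, as a minor inconsistency. The 80% stated for 8 and 15 recordings per arm belongs to a single unadjusted test. For the planned Holm-adjusted test of the total score, power at those sizes is about 35–41% by the t method and 46–58% by a normal approximation. This rests on 16 to 21 tests, the SAP's difference of 5 and SD of 5, and a shift spread evenly over the questions. It does not show that the study is underpowered, since the planned 100 recordings are ample. Confidence in the mismatch is high; the exact power depends on the number of subgroups and on the reference distribution, neither of which the SAP states.

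**What to change.** Before any scores are analysed, the sponsor should choose one of two options.

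1. **Test the total first.** Test the total score at two-sided 0.05, and apply Holm to the questions and subgroup totals only if it is significant. Family-wise error stays at 0.05. The 8 and 15 then apply at SD 5 (9 and 18 at SD 5.48). The cost is that question and subgroup results are descriptive if the total is not significant.
2. **Keep one Holm family.** State the number of tests and restate the minimum recordings per arm at SD 5: 14 (rho 0.1) and 28 (rho 0.8) for 16 tests, or 15 and 29 for 21. Note that SD 5.48 needs 17 and 33, or 17 and 34. For 16 tests, the minimum number of ratings rises from 48 and 90 to 14·3·2 = 84 and 28·3·2 = 168 at SD 5, or to 17·3·2 = 102 and 33·3·2 = 198 at SD 5.48. All are below the 100·3 = 300 ratings already planned.

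Under either option, state n_record in the SAP, consistent with the Protocol's 100. The change is one or two sentences and needs no recordings beyond those planned.

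### The SAP's power calculation uses a total-score SD of 5, but the simulation it describes gives 5.48; power at 8 and 15 recordings per arm is then about 77% and 74%, not 80%

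*SAP*

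**What the plan says.** The SAP's Power calculations section sets its target this way: "To achieve 80% power at a 0.05 level when the true mean difference is 5 and standard deviation of 5". With three ratings per recording, it concludes that 8 recordings per arm are enough if the intra-recording correlation is 0.1, and 15 per arm if it is 0.8.

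The closing paragraph of that section explains the inputs. They rest on "simulated ordinal 5-level data (with a uniform distribution across levels) generated 15 times (one for each question" and summed over many realizations. The result is given as: "This leads to an approximate distribution of total scores with mean 45 and standard deviation 5".

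Three other places bear on the point:

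- The SAP's opening description says of the questionnaire: "These questions fit into logical groupings to assess different aspects of equity and respect during the recruitment conversation".
- The Analysis Plan states that "we take the total of the question scores to be continuous", so the SD of that total drives the power calculation.
- The SAP does not fix how many recordings will be rated. Its first planned figure will report the "number of videos sampled for assessment". Protocol section 7.4 plans 100 audio recordings.

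**The concern.** The SD reported in the SAP is not the SD that its described simulation produces. The gap looks small, but power depends on the ratio of the difference to the SD, and the stated sample sizes have little slack. A modest understatement of the SD is enough to take both scenarios below 80%.

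This section is the SAP's only sample-size reasoning, and the number to be rated is left open. Someone deciding how many recordings to send to the three raters has only the 8 and 15 to rely on.

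A second, conditional matter is that the described simulation mentions no correlation between questions, although the questions are grouped by shared aspect and then summed. Positive correlation would widen the distribution of the total. The SAP gives no range of SDs that would show how much this matters.

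**Working it through.** **Inputs from the SAP.** Difference 5 points; SD 5; alpha 0.05; target power 80%; 3 ratings per recording; equal arms; intra-recording correlation ρ = 0.1 or 0.8; 15 items, each uniform on five levels. The SAP does not say whether the test is one- or two-sided. Two-sided is assumed, because it reproduces the stated figures and one-sided does not (a one-sided normal approximation gives 5 and 11 per arm).

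**Step 1: reproduce the SAP's figures at SD 5.** With n recordings per arm and 3 ratings each,

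SE of the difference = SD × √[2(1 + 2ρ)/(3n)],

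and power comes from the noncentral t with 2(n − 1) degrees of freedom and noncentrality 5/SE.

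- ρ = 0.1, n = 8: SE = 5 × √(2.4/24) = 1.581; noncentrality 3.16; power 83.6%. At n = 7 power is 77.5%.
- ρ = 0.8, n = 15: SE = 5 × √(5.2/45) = 1.700; noncentrality 2.94; power 81.0%. At n = 14 power is 78.1%.

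The smallest n reaching 80% is 8 and 15, exactly as stated. A plain normal approximation gives 7 and 14; adding one cluster per arm as a small-sample correction also gives 8 and 15.

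**Step 2: the SD from the described simulation.** A uniform 1–5 item has mean 3 and variance (25 − 1)/12 = 2. Fifteen independent items have mean 15 × 3 = 45, which matches the SAP, and SD √(15 × 2) = √30 = 5.48, which does not. One million simulated totals gave mean 45.00 and SD 5.477. The matching mean confirms 15 items scored 1–5, so a different item count or scoring does not explain the gap.

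**Step 3: change only the SD.**

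| Scenario | SE | Noncentrality | Power at stated n | n for 80% | Power at that n | Detectable difference at stated n |
|---|---|---|---|---|---|---|
| ρ = 0.1, n = 8 | √(30 × 0.1) = 1.732 | 2.89 | 76.6% | 9 | 82.0% | 5.2 |
| ρ = 0.8, n = 15 | √(30 × 0.1156) = 1.862 | 2.69 | 73.6% | 18 (17 gives 79.2%) | 81.5% | 5.4 |

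Total observations become 9 × 3 × 2 = 54 and 18 × 3 × 2 = 108, against the SAP's 48 and 90. An item-level simulation (15 independent uniform items, three correlated raters, t test on conversation means, 20,000 runs) agrees: 76.8% and 73.3% at 8 and 15 per arm; 81.9% and 81.1% at 9 and 18.

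**Step 4: how much rounding the plan can bear.** The largest SD that still gives 80% is 5.25 at 8 per arm (ρ = 0.1) and 5.07 at 15 per arm (ρ = 0.8). Both are below 5.48.

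**Step 5: correlated questions (assumed values).** With item variance v and a common inter-question correlation r, the SD of the total is √[15v(1 + 14r)]. The documents give neither v nor r, so these rows are illustrations.

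| v | r | SD | Power, 8 per arm, ρ = 0.1 | Power, 15 per arm, ρ = 0.8 |
|---|---|---|---|---|
| 2 (uniform) | 0.1 | 8.5 | 41% | 39% |
| 2 (uniform) | 0.3 | 12.5 | 22% | 21% |
| 1 | 0.1 | 6.0 | 69% | 66% |
| 1 | 0.3 | 8.8 | 39% | 36% |
| 0.7 | 0.1 | 5.0 | 83% | 81% |

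At v = 1, 80% holds only up to r of about 0.06 (8 per arm) or 0.05 (15 per arm).

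**Step 6: the Protocol's 100 recordings.** Assume 50 per arm, all rated. At SD 5.48 power is above 99% at both ρ values, with a detectable difference of 2.0 points (ρ = 0.1) or 2.9 points (ρ = 0.8). At r = 0.3, power at ρ = 0.1 and 0.8 is 88% and 57% for uniform items, or 99% and 85% for item variance 1.

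**The case against.** The strongest reply has five parts.

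1. *The SAP calls the distribution approximate, so 5 is a coarse planning value.* The power step itself is right for SD 5; the slip is one step earlier. That stands as a description of where the error arose. It does not rescue the 80%: going from 5.48 to 5 cuts the variance from 30 to 25, about 17%, and 5.48 is beyond the tolerance in both scenarios.

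2. *Power depends only on difference/SD, which the SAP sets at 1.* If the 5 points were meant as one SD, correcting both would leave 8 and 15 unchanged. The SAP gives no separate justification for 5 points, so this reading cannot be excluded. As written, though, the SAP states a 5-point difference, and the result here is conditional on that.

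3. *The method is inferred.* Under a plain normal approximation, SD 5.48 gives 82.3% at 8 per arm, still above 80%. But that approximation does not reproduce the SAP's 8 and 15. It also gives only 76.6% at 15 per arm and needs 17, so the ρ = 0.8 scenario fails under either method.

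4. *The correlation results rest on the reviewer's values.* This is correct. One assumed pair even restores SD 5 and keeps 80%. They support asking for a sensitivity range and nothing stronger.

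5. *Nothing in the design is shown to change.* The study is a feasibility pilot, 8 and 15 are not fixed as targets, and 100 recordings would be ample at SD 5.48. This limits the practical weight. It does not make the stated requirement correct, and the number to be rated remains open.

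**Conclusion.** The point holds. The described simulation gives an SD of 5.48, not 5. At 5.48 the stated 8 and 15 recordings per arm have about 77% and 74% power, and 9 and 18 are needed for 80%. Put as a detectable difference, the change is from 5 points to 5.2 and 5.4.

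This rests on four assumptions: items generated independently, which is the natural reading of the SAP; a two-sided test; the t-based calculation, which matches the SAP's figures exactly; and a difference held at 5 points.

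Any further loss from correlated questions is conditional on values the documents do not give. The error should be fixed because it sits in the SAP's only sample-size reasoning, but it is modest and does not show that the planned 100 recordings are too few.

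**What to change.** In the SAP's Power calculations section:

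- Correct the SD to 5.48 for independent uniform items. Restate the requirement as 9 and 18 recordings per arm, or keep 8 and 15 and state the power as about 77% and 74%.
- Say whether the 5-point difference is a fixed number of points or one SD, and name the formula and the sidedness of the test.
- Rerun the simulation over a stated range of inter-question correlations and item variances.
- State how many recordings will be rated, and report power or the smallest detectable difference at that number for both ρ = 0.1 and ρ = 0.8.

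The cost is SAP wording and a rerun of the simulation. The stated figure becomes slightly less favourable. No extra enrolment is needed.
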